### 3.2 Inclusion criteria

Each patient must meet all of the following criteria to be enrolled in this study:

1. The patient has a histologically or cytologically-confirmed diagnosis of squamous cell carcinoma of the head and neck (excluding carcinomas of the nasopharynx types II and III according to the World Health Organization criteria), for whom surgical resection of the tumor is planned as part of the treatment. Patients with skin squamous cell carcinomas of the head and neck region will also be included in this study.
2. There is availability of a baseline, paraffin-embedded, tumor specimen for biomarker evaluation. No anti-neoplastic treatment is allowed between the time from obtaining the baseline tumor specimen and randomization. If a baseline tumor specimen is not available, a biopsy of the tumor will be performed prior to randomization.
3. Prior treatment with biological agents targeted to the epidermal growth factor receptor is allowed, provided the time from last exposure to this treatment was  $\geq$  6 months.
4. The patient has a fasting serum glucose  $<$  130 mg/dL and HbA1C  $\leq$  7.0%. Patients with a history of diabetes mellitus are allowed to participate, provided that they are on a stable dietary or therapeutic regimen for this condition.
5. The patient has adequate renal function, defined by serum creatinine  $\leq$  1.5 x the institutional upper limit of normal (ULN), or creatinine clearance  $\geq$  60 mL/min for patients with creatinine levels above the ULN
6. Because the teratogenicity of cetuximab and IMC-A12 is not known, women of childbearing potential and men must agree to use adequate contraception (hormonal or barrier method of birth control; abstinence) prior to study entry and for the duration of study participation.
7. The patient is age  $\geq$  18 years.
8. The patient or the patient's legally authorized representative has the ability to understand and the willingness to sign a written informed consent document.
9. ECOG performance status of 0-2

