### 6.5 *Clinical laboratory tests*

The blood-based clinical laboratory tests will include:

- Hematology profile: complete blood count with differential and platelet count
- Chemistry profile: fasting glucose, creatinine, aspartate aminotransferase (AST), alanine aminotransferase (ALT), lactate dehydrogenase (LDH), alkaline phosphatase, total bilirubin, sodium, potassium, carbon dioxide, magnesium, and amylase
- Pregnancy test: serum or urine pregnancy test

- Additional tests: 26 mL of blood will be collected and stored for additional studies of interest, including (but not restricted to) fasting insulin, fasting peptide C, triglycerides, fasting free-fatty acids and evaluation of blood-based biomarkers (refer to section 6.9.3). Briefly, blood will be collected using one EDTA (10 mL) tube and two 9-mL CPT tubes for blood cells separation and storage. Samples will be forwarded to the core laboratory to be processed within one hour of collection. Blood will be centrifuged in a standard clinical centrifuge at 2500 RPM at 4 °C for 10 minutes. Aliquots of 2.0-2.5 mL of serum should then be transferred into 2 (two) cryovials, labeled with the protocol number and the patient's unique study identification number. Cryovials will be stored at -80 °C. Peripheral blood cells will also be stored at -80 °C.

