#### **6.10.3 Blood-based biomarkers**

Blood will be obtained at baseline, before the second treatment with the study drug(s), before surgical resection, and within 30 days after surgery, preferably in the morning, after at least 12 hours of fasting. The blood samples will be stored for the evaluation of biomarkers indicative of, or predictive of activity and / or toxicity of the investigational agents. These may include (but are not restricted to): free and total IGF-1 and IGF-2, IGFBP-3, insulin, peptide C, free fatty acids, triglycerides, fructosamine, a panel of 59 cytokine and angiogenic factors measured by available luminex multiplex beads kits (Bio-Plex 27-Plex & 23-Plex Kits [Bio-Rad, Hercules, CA] and Human CVD Biomarker Panel 1 kit [Linco Research, Inc., St. Charles, MOsa]), VEGF, solubleVEGFR-1, soluble VEGFR-2, osteopontin, high-throughput proteomic analysis, genomic analysis and other biomarkers that may emerge to be important for characterization of cetuximab and/or IMC-A12 activity and/or toxicity. Correlation of these biomarkers with efficacy and toxicity outcomes will be analyzed in an exploratory fashion.

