## **7.3 *End of therapy***

Vital signs and clinical laboratory tests (as described in sections 6.4 and 6.5) should be obtained preferably on the day of surgery, or within 2 days before surgery.

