## **7.4 *Follow-up***

One post-operative evaluation should be completed within 30 days after surgery. At this time, a medical history, physical examination, vital signs (as described in sections 6.2, 6.3, 6.4), adverse events assessment (as described in section 8), and optional blood-based biomarkers (as described in section 6.5) should be obtained. Alternatively, a telephone call to assess adverse events may substitute for a medical history, physical examination, and vital signs in the event the patient is not evaluated by the investigator or his/her designee within 30 days after surgery. Audiometric evaluation should be obtained within 90 days after surgery in all patients who received at least one dose of IMC-A12 (as described in section 6.8). If toxicities related to the investigational drugs have not been resolved at the time of the post-operative evaluation, regular follow-ups are strongly

enforced with frequency to be determined by the investigator. After the end of therapy, patients should continue to be assessed by their primary physicians for long-term follow-up. Data on progression-free survival, and possible long-term toxicities will be retrospectively obtained through chart reviews. Patients (or their family members) might also be contacted (during clinic visits, by telephone, in writing, or electronic mail) to confirm or provide information on long-term follow-up.

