## 7.5 Study events table

Procedure	Pre-Treatment Evaluations	Treatment Period	End of Therapy	Follow-Up
	(within 30 days before first dose of treatment)	(within 5 days before second and third dose of treatment)	(day of surgery, preferably, or within 2 days before surgery)	(within 30 days after surgery)
Eligibility Assessments				
Informed Consent	X 			
Inclusion/Exclusion Criteria	X			
Medical History and Physical Examination	X			
Pregnancy Test	X			
Safety Assessments				
Medical History and Physical Examination 		X		X 
Vital Signs (blood pressure, heart rate, temperature)	X	X	X	X 
Toxicity Assessments/Adverse Events	X	X		X 
Laboratory Tests				
Hematology Profile	X	X	X	
Serum Chemistry Profile	X	X	X	
Imaging studies				
CT Scan or MRI of the H&N	X		X 	
Audiometry	X 			X 
Pharmacodynamic Assessments				
Tumor specimen biomarkers	X 		X	
Skeletal muscle/adipose tissue biomarkers 			X	
Blood-based biomarkers 	X	X 	X	X

 Informed consent should be obtained prior to registering for trial, undergoing protocol-specific evaluations, or receiving treatment.

 Initial medical history should include past or current medical conditions, current medications, date of diagnosis, stage (using the American Joint Committee on Cancer Staging Manual, Sixth Edition or higher), pathological confirmation of HNSCC and tentative date of surgery (if available). Any pre-existing toxicity should be documented and recorded as well. The physical examination will include an evaluation by pertinent body system, height (pretreatment only), weight, and body surface area (BSA), as well as ECOG performance status (pretreatment only) should be documented.

 26 mL of blood (optional) will be collected and stored for additional studies of interest

 May be obtained at any time-point between the last dose of the study drug(s) and the surgical procedure. However, preferably, scans will be performed the day before surgery.

 Baseline tumor tissue may be obtained more than 30 days prior to treatment initiation.

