## **12.5 Statistical analysis**

Modulation of phospho-Akt (difference in IHC score between the surgical specimen and the baseline biopsy) and other biomarkers will be compared between any two of the three treatment arms with the use of Wilcoxon rank sum test. Further evaluations will adjust

comparisons of follow-up marker values for baseline values, when available, using analysis of covariance. Prior to analysis by parametric methods (such as analysis of covariance), we will assess the data for the need for transformation to normality, transforming where appropriate. We will use repeated measures analysis of variance to analyze endpoints that are observed at multiple time points (e.g. serum glucose). Spearman's rank correlation test will be used to investigate the relationship between different biomarkers and between biomarkers and toxicity. Correlations of categorical variables will be assessed by Fisher's exact test. A type I error rate of 0.05 (two-sided test) will be used for all comparisons.

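### The repeated measures ANOVA named for serial endpoints does not suit uneven chemistry visits and optional research blood; a mixed model would use partial series at almost no cost

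*Combined protocol and SAP*

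**What the plan says.** Section 12.5 gives one method for every serial endpoint: "We will use repeated measures analysis of variance to analyze endpoints that are observed at multiple time points (e.g. serum glucose". It does not name the time points, the covariance structure, the covariates for this analysis or the handling of missing values. It also does not say that patients with a gap are excluded.

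Two kinds of serial blood measurement fall under that sentence, and their schedules differ.

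- **Fasting glucose.** Section 6.5 puts it in the routine chemistry: "Chemistry profile: fasting glucose, creatinine, aspartate aminotransferase (AST), alanine aminotransferase (ALT". A baseline value is needed for entry, since a criterion in section 3.2 ("The patient has a fasting serum glucose") sets an upper limit on it. In the study events table (section 7.5) the treatment-period column is headed "within 5 days before second and third dose of treatment", whereas section 7.2 asks for laboratory tests before the second treatment only. At end of therapy, section 7.3 says the tests "should be obtained preferably on the day of surgery, or within 2 days before surgery". The table marks no chemistry at follow-up.
- **Research blood** (insulin, peptide C, free fatty acids, IGF-related markers, cytokines). Footnote 3 of the table reads: "26 mL of blood (optional) will be collected and stored for additional studies of interest". Section 6.10.3 sets four draws: "Blood will be obtained at baseline, before the second treatment with the study drug(s), before surgical resection, and within 30 days after surgery". Section 7.4 again marks the last one as a matter of choice: "optional blood-based biomarkers (as described in section 6.5) should be obtained". Footnote 7 limits the on-treatment draw to the one before dose 2, so a third dose does not alter this schedule.

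Under section 4.1 a third dose, about a week after the second, arises only when the operation is put off.

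**The concern.** Classical repeated measures ANOVA works on a full rectangle: every patient measured at the same set of times. A patient with an empty cell has to leave the analysis or have the cell filled in. A value taken at a visit that other patients do not have cannot be placed.

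Both situations can arise here. Patients whose surgery is delayed may have one more glucose value than the others, and their pre-surgery value comes about a week later and after three doses instead of two. Research samples can be declined draw by draw.

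Effects on glucose metabolism are a listed secondary objective (section 2.2), and section 1.4.5 relies on the research blood to judge insulin secretion and insulin resistance. With 20 patients per arm, discarding partial series costs visible precision. Because section 12.5 is silent on gaps, the choice would be made after the data are seen. Use of anti-hyperglycemic drugs, a stratification factor in section 3.5 that bears directly on glucose, is also absent from the stated analysis.

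**Working it through.** **1. The plan's own figure.** There is none for the serial endpoints. The 20 per arm comes from the primary comparison (section 12.4) and reproduces. With the stated probability of 0.856, a Bonferroni level of 0.05/3 two-sided and 90% power, Noether's formula gives a two-arm total of (2.394 + 1.282)² / (3 × 0.356²) = 13.51 / 0.380 = 35.5. That is 17.8 per arm, rounded up to 18, and 18 / 0.90 = 20 with the Synopsis's 10% inevaluable rate. This does not depend on how serial data are analyzed.

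**2. The two schedules side by side.**

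| Time | Fasting glucose | Research blood |
|---|---|---|
| Baseline | Yes, required for entry | Optional |
| Before dose 2 | Yes | Optional |
| Before dose 3 (if given) | Yes in 7.5; not mentioned in 7.2 | Not drawn |
| Before surgery | Yes | Optional |
| Within 30 days after surgery | Not scheduled | Optional |

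The uneven visit affects glucose only, and the optional status affects research blood only.

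**3. Patients with complete series.** Let m be the chance that a draw is missing and k the number of draws that can be missed. The documents give no m, so 10% and 20% are assumptions, and draws are taken as independent. The complete share is (1 − m)^k.

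| Endpoint | k | m = 10% | m = 20% |
|---|---|---|---|
| Glucose, baseline present, no third dose | 2 | 0.81, or 16.2 of 20 | 0.64, or 12.8 of 20 |
| Research blood, all four draws | 4 | 0.656, or 13.1 of 20 | 0.410, or 8.2 of 20 |
| Research blood, baseline present | 3 | 0.729, or 14.6 of 20 | 0.512, or 10.2 of 20 |

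**4. Patients with at least one post-baseline value.** This share is 1 − m^k. For glucose (k = 2) it is 0.99 and 0.96, or 19.8 and 19.2 of 20. For research blood with baseline present (k = 3) it is 0.999 and 0.992, or 20.0 and 19.8 of 20.

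**5. Information kept relative to full data.** A simulation took 20 per arm, baseline always present, compound symmetry with correlation 0.3 to 0.7, and values missing completely at random. It compared complete cases with generalized least squares on all values, for the arm difference in mean post-baseline change.

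| Post-baseline draws | m | Complete cases | All available values |
|---|---|---|---|
| 2 | 10% | 0.80 | 0.94–0.95 |
| 2 | 20% | 0.62 | 0.88–0.90 |
| 3 | 10% | 0.71 | 0.96–0.97 |
| 3 | 20% | 0.48–0.49 | 0.92–0.93 |

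The covariance was treated as known, so a fitted mixed model would gain somewhat less.

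**The case against.** **The plan does not prescribe complete cases.** A reader might infer that it drops every patient with a gap. It does not say so: exclusion is a property of the classical method, and an analyst could fit the same mean structure by likelihood. This stands. But section 12.5 does not say that either, and the name it uses ordinarily means the complete-data method.

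**Glucose is not optional.** A reader might carry the optional label, or the 13 and 8 of 20, over to glucose. The label belongs to the 26 mL research sample, and those figures to its four draws. Nor does telephone follow-up cost glucose values: no chemistry is scheduled then, and the call is said to replace history, examination and vital signs, not blood.

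**Bias is not shown.** A reader might infer that gaps concentrate in patients with toxicity. Dosing does depend on toxicity (sections 9.2.2, 10.1 and 10.2), but the last chemistry draw is tied to surgery and not to a dose, and nothing in the documents shows who would miss draws. Biased comparison is possible, not established. A mixed model is itself valid only if missingness depends on observed data.

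**Optional samples may be refused as a block.** If so, there are fewer partial series than under independence, and the gain shrinks. A patient with no samples contributes nothing to either analysis. This stands.

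**Other analyses remain.** The pairwise Wilcoxon tests and analysis of covariance in section 12.5 can still use a patient with one missing draw, and toxicity is analyzed in the safety population. This lowers the stakes, but does not make the named serial method as good as the alternative.

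**Conclusion.** The point holds in a limited form. For glucose, the mismatch is the pre-third-dose value that only some patients have, plus any missed draw. At an assumed 10% or 20% missing per post-baseline draw, about 16 or 13 of 20 per arm would have both post-baseline values. For research blood, about 13 or 8 of 20 would have all four samples at the same rates. These counts rest on independent missingness; the documents supply neither missingness rates nor the frequency of a third dose, so the actual loss cannot be sized. The documents do not support the stronger reading that glucose sampling is optional, that exclusion is written policy, or that a mixed model would retain every patient. The affected endpoints are secondary or exploratory, and the primary phospho-Akt comparison is unchanged. Label: cheap improvement.

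**What to change.** Replace the sentence in section 12.5 with a likelihood-based linear mixed model for repeated measures that uses all available measurements. Specify:

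- **Terms:** arm, time, arm by time, baseline value and the two stratification factors from section 3.5, with a named within-patient covariance structure and a small-sample degrees-of-freedom correction.
- **Visits:** for glucose, baseline, before dose 2 and before surgery; for research blood, these and the draw within 30 days after surgery.
- **The pre-third-dose chemistry value:** how it enters, for example by actual day from first dose.
- **Baseline research blood:** treated as part of the response vector, so that a missing baseline does not remove the patient.
- **Missing data:** the missing-at-random assumption, stated openly, with counts of available samples by arm and visit.

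Sections 7.2 and 7.5 must also be reconciled on whether chemistry is drawn before a third dose.

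The cost is a few sentences and standard software, with no extra data. The small downside is reliance on missing at random and more modelling choices at about 20 patients per arm, which is why they should be fixed in advance.

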## **12.6 *Interim analysis***

### **12.6.1 *Interim efficacy analysis***

No formal interim analysis of efficacy is planned.

### **12.6.2 *Interim safety analysis***

The combination of cetuximab and IMC-A12 has not been extensively assessed in human subjects. Because of the different anticancer mechanisms and non-overlapping clinical toxicities of these agents, it is not anticipated that the toxicity of this combination therapy will significantly exceed that observed with IMC-A12 or cetuximab monotherapy or present an undue risk to patients. Additionally, the combination of cetuximab and IMC-A12 was not associated with enhanced toxicity in preclinical in vivo studies.

Nonetheless, the potential for unforeseen or additional toxicity exists with any novel combination. Hence, as added precautions, in the event that new safety signals are detected, or the incidence of serious adverse events exceeds that expected of the component drugs within the combination therapy, consideration will be given to protocol modification, termination, or additional safety review at specified time-points before accrual is completed.

A Bayesian toxicity monitoring rule will be applied in each arm separately to ensure patient safety. However, all toxicities across all arms will be examined together as well for identifying the patterns of toxicity to provide further protection of patient safety. It is defined that an acceptable target toxicity level is no more than 30% of the patients experiencing dose limiting toxicity (DLT, defined as grade 3–4 toxicities, except for hypersensitivity reactions and grade 3 skin toxicity and fatigue). If at any given time, the probability that the DLT rate exceeds the 30% target is high (probability  $> 0.8$ ), consideration will be given to modifying the protocol accordingly. Assuming that the probability of DLT has a vague prior of beta (0.3, 0.7), the posterior distribution of the DLT rate is also a beta. The “stopping boundaries” (i.e., holding for new patients randomization) are 3/6, 4/8, 5/11, 6/14, 7/17, and 8/20 where “a”/“b” indicates “a” patients experiencing a DLT among the first “b” patients. In other words, in each given arm we will hold randomization for new patients if the number of DLTs given the number of patients treated is **greater than or equal to** the boundaries indicated above.

## 13 Administrative considerations

### 13.1 *Institutional review board approval*

The IRB must operate in accordance with 21 Code of Federal Regulations Part 56 and other appropriate governmental regulations. Before study initiation, the investigator must have specified written and dated approval from the IRB/aEC for the protocol, consent form, and patient recruitment materials/process (e.g., advertisements).

The investigator should provide the IRB/aEC with reports, updates, and other information (e.g., safety updates, amendments, and administrative letters) according to regulatory requirements or institution procedures.

### 13.2 *Ethical conduct of the study*

This study will be conducted under a United States (US) IND, and the findings of this study are expected to significantly contribute to subsequent regulatory submissions. Therefore, US FDA regulations (21 Code of Federal Regulations [CFR] Part 56 and Part

312), International Conference on Harmonization (ICH) guidelines, Eli Lilly & Co. and ImClone Systems policies require the investigator to be aware of his/her obligations in the conduct of this study.

This study will also be conducted in accordance with the ethical principles included in the "Recommendations Guiding Physicians in Biomedical Research Involving Human Subjects" adopted by the 18th World Medical Assembly, Helsinki, Finland, June 1964, and amended by the 29th World Medical Assembly, Tokyo, Japan, October 1975; the 35th World Medical Assembly, Venice, Italy, October 1983; the 41st World Medical Assembly, Hong Kong, September 1989; the 48th General Assembly, Somerset West, Republic of South Africa, October 1996; and the 52nd World Medical Assembly, Edinburgh, Scotland, October 2000 and will conform to any more current revisions to these principles.

### ***13.3 Compliance with the protocol and protocol revisions***

The investigator must comply with all requirements of the protocol. When a situation occurs that requires a temporary departure from the protocol, the investigator will describe the departure from the protocol and the circumstances requiring it on the patient's medical record and will notify the IRB/aEC as appropriate.

Patients may not be enrolled in an amended protocol until that amendment has been IRB/aEC approved.

### ***13.4 Patient information and consent***

Written informed consent will be given by each patient before entering the study, in accordance with US Title 21 CFR Parts 50.20 through 50.27 and the current edition of the Declaration of Helsinki, as well as Good Clinical Practices (GCPs).

Investigators must ensure that patients are clearly and fully informed about the purpose, potential risks, and other critical issues regarding clinical trials in which they volunteer to participate.

### **13.4.1 Informed consent procedures**

Preparation of the consent form is the responsibility of the investigator and must include all elements required by the ICH, GCP, and applicable regulatory requirements and must adhere to GCP and the ethical principles that have their origin in the Declaration of Helsinki. Prior to the beginning of the study, the investigator must have the IRB/aEC's written approval/favorable opinion of the written informed consent form and any other information to be provided to the patients.

The investigator must provide the patient or legally acceptable representative with a copy of the consent form and written information about the study in the language in which the patient is most proficient. The language must be nontechnical and easily understood.

The investigator should allow time necessary for patient or patient's legally acceptable representative to inquire about the details of the study, informed consent must be signed and personally dated by the patient or the patient's legally acceptable representative and by the person who conducted the informed consent discussion. The patient or legally acceptable representative should receive a copy of the signed informed consent form and any other written information provided to study patients prior to the patient's participation in the trial.

